tests, partly for serum concentration determination. They are also informed that they will receive at least 1 year of follow-up in RVD, against the usual ½ year. At the visit after 1 year, the same clinical tests and scales are carried out as during the patients' preliminary examination, and matters relating to compliance are queried. The other group (intervention group) will have an extra blood sample taken if they experience side effects from the treatment within the first 2 months. Everyone also has one extra blood test at each The ½- and 1-year check-ups. In addition, they will also be followed for at least 1 year against the normal ½ year. At the 1-year check-up, the same clinical tests and scales are carried out as in the pre-examination, and matters relating to compliance are queried. Subsequently, the respective compliance, distribution of serum concentrations, as well as the importance of serum concentration determination and derived dose regulation for the overall clinical response after 1 year (assessed on MMSE, ACE, NPI, DAD and CGI). A comparison is made of the occurrence, duration and outcome of side effects in the 2 groups, including the proportion of patients who had to change preparations or abandon medical treatment due to side effects. The project manager (alternatively the person performing the test) is blinded in relation to which group the patient is randomized to and to the result of serum values. The final statistical analysis of the clinical value of serum determinations and derivative monitoring is performed by an independent statistician. No participants will receive any form of remuneration for participation in the project. Any additional costs for transport are covered according to the appendix. Use of journal information Journal information is used to identify the target group, including clarifying inclusion and exclusion criteria (see these). During the project period of one year, the journal is used to document and monitor any side effects or unintended events, just as all possible side effects or unwanted events are entered into the patient's CRF.

FLOWCHART FOR PROJECT "MONANTI"

Inclusion criteria for participants

- All patients [evaluated at RVD] who after diagnostic assessment has been completed, meet the criteria for
- Alzheimer's Dementia (AD), (NIA-AA, (1)), Dementia with Lewy-Bodies (DLB) (15) or Parkinson's Disease Dementia (PDD) (18), and
- who are scheduled for treated with Donepezil or Memantine and

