- who give informed consent to participation.

Both patients with mild-moderate dementia and patients with moderate to severe dementia are enrolled, because we want to explore whether the correlation between effect and serum concentration varies depending on the stage of dementia.

Exclusion criteria for participants

- Patients not accompanied by relatives to study visits.
- Patients who live alone and do not have help with the medication administration
- Inability to cooperate to testing, also severely impaired vision or hearing, amputation or other severe disabilities.
- Inability to meaningfully give informed consent due to cognitive impairment.
- Patients with known underlying psychiatric illnesses (schizophrenia, bipolar affective disorder, etc.). Depression is permitted if the patient has been on regular medical treatment for at least 3 months prior to inclusion.
- Patients with known neurological conditions (MS, epilepsy, brain tumors etc.), which in themselves could be contributing to the patients cognitive symptoms.
- Patients with medical conditions (kidney, liver, metabolic etc.) which in themselves could be contributing to the patients cognitive symptoms.
- Patients who, currently or in the past 3 months before enrollment, have been treated with anti-psychotics or neuroleptics. Minimal doses of benzodiazepines or hypnotics are accepted.
- Patients with previous heavy abuse of alcohol or illegal drugs, or any abuse within the last 3 months before inclusion.

- Patients with previous severe head trauma or neuroinfections, which in themselves could contribute to the patients cognitive symptoms.
- Patients who have had ECT [Electro Convulsive Therapy] treatment within the last 3 months.
- General anesthesia within the last 3 months.

Withdrawal criteria for all

- The participant or relative wishes to withdraw from the study.
- Symptoms deemed unacceptable by the physician responsible for the trial in accordance with the above exclusion criteria.
- Medical reasons, including if the treatment is changed to an anti-dementia drug for which serum concentrations are not measured in this study [galantamin or rivastigmine].

Study execution and visits

Inclusion interview/recruitment

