- At the weekly interdisciplinary diagnostic conference at RVD, all eligible patients are noted. An anonymized list is kept, which ensures that all patients who meet the criteria for participation are offered participation. An anonymized list of both included and non-included patients is maintained continuously [screening list].
- Inclusion criteria are assessed.
- Exclusion criteria are assessed.
- If the patient meets the criteria, participation in the project is offered at the information visit [the visit during which the diagnosis is presented to the patient]. Written information is provided and time to reflect on the offer of study participation is provided.
- Possible participants are contacted by telephone within one week, and those who wish to participate are immediately invited to an enrollment visit.

- Patient and accompanying relatives are informed both orally and in writing about the study's purpose, background, execution and any side effects/possible harms of participation.
- The patient is again offered time to reflect.
- If the patient wishes to participate, a declaration of consent [must be] signed [by the patient].
- Randomization is carried out to control or intervention group. The participant and the relative are informed via the project nurse about which group they have been allocated to.
- The participant is registered in the Case Report Form (CRF).
- The project nurse registers the participant's trial number [randomization number], which will be the only identification for the subsequent examinations (for reasons of blinding).
- A blood sample for genetic analysis is taken from all participants.
- Participants in the intervention group are offered an extra blood test if side effects develop within 2 weeks to 2 months after starting treatment. The dose is adjusted in relation to the serum concentration, if necessary the dosage and/or drug prescribed is changed. At the ½-year follow-up, one extra blood test is collected for all participants. The dosage is adjusted according to the serum concentration, if deemed appropriate an alternative [anti-dementia] drug is prescribed.
- Participants belonging to the control group will not undergo any extra procedures, apart from a single blood test at the end of the project.

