- Approx. 30 patients will have a standard EEG with modified photo-block performed, if Donepezil treatment has not been started beforehand. These approx. 30 patients will have another standard EEG performed with the same modified photo-block approx. one year later in connection with the point below.
- After one year, all participants are called for one additional visit. Here, a blood test is carried out on all participants, just as all participants are offered a dosage adjustment depending on the serum concentration, also if appropriate a change of preparation. The same clinical tests are carried out as during the preliminary examination [or enrollment visit]. All participants are asked about treatment compliance.

- If there is a need for dose adjustment or possibly prescription change during the project, the decision will be made by the person in charge of the experiment [primary investigator] and not the project manager (PhD student). Practical handling is carried out in collaboration between the project manager and the project nurse.
- A blinded calculation of the distribution of serum concentration, clinical scores, compliance and occurrence of side effects [is done by a statistician not affiliated with the study]

Study visits

- In connection with the information interview, as part of the general clinical course, the initial information about the project is provided and project information is provided.
- Potential participants are contacted to participate in one extra visit (inclusion interview with project manager) together with the relative.
- If informed consent is obtained, one extra visit to the clinic 1 year after enrollment ["1 year follow-up visit"]. The visit ½ year after enrollment is part of the routine follow-up at RVD.

End of study

The study is ended on the date when the last participant (cf. power calculation) has been evaluated at the 1-year follow-up visit. Subsequently, after registration and [external] monitoring [of data quality], data will be transferred to blinded statistical analysis by a statistician. A need for future follow-up visits will be conducted at the GPs office.

Study design

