- Unexpected (i.e. inconsistent with common knowledge about potential side effects)
- There is at least a reasonable possibility that there is a causal connection between the incident and the procedure will be classified as Suspected Unexpected Serious Adverse Reactions (SUSAR).

The assessment of the relationship between an adverse event and the procedure (probable, possible, unlikely, none, cannot be assessed) is a clinical decision based on all available information. Factors that should be considered in the relationship assessment include the temporal sequence from the time of the procedure, improvement upon cessation (withdrawal) of the procedure, underlying concurrent competing illnesses, concurrent medical procedures or treatment, known pattern of response to methods used, exposure to physical and/or psychological stress. The physician in charge of the study, senior doctor [consultant] [name], is responsible for evaluating whether an adverse event

is serious or not and, in case of doubt, relevant information will be obtained and reported in detail. The product summaries for Donepezil and Memantine are used to assess whether a serious related side effect is expected. All adverse events in connection with the experiment will be registered and reported, cf. legislation, to the authorities. The sponsor is required to ensure that all information about SUSARs, which are fatal or life-threatening, is registered and reported to the Danish Medicines Agency as soon as possible and no later than 7 days after the sponsor has become aware of such a suspected side effect. No later than 8 days after the report, the sponsor must notify the Danish Medicines Agency of all relevant information about the sponsor's and investigator's follow-up to the report. All other SUSARs must be reported to the Danish Medicines Agency no later than 15 days after the sponsor has become aware of them.

Monitoring subjects with adverse events

All adverse events that occur during the study must be monitored and followed until they have either resolved, returned to normal or baseline values, reached clinical stability, or been shown to be unrelated to the project.

Ethical considerations

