In accordance with current regulations, the protocol was approval by the Regional Scientific Ethics Committee for Region Zealand and the Danish Data Protection Agency [Datatilsynet]. The project was approved by the Danish Medicines Agency and registered at www.clinicaltrials.gov. It will also be monitored externally by the GCP unit at Copenhagen University Hospital.

Insurance

All complaints during the study or possible damage to the test subjects will be handled in accordance with the Danish law on access to complaints and compensation within the healthcare system. The subjects are covered by the [Danish] Patient Insurance [Danish: 'Patientforsikringen'].

Time schedule

The first participant was recruited on 12 February 2020. The last participant was recruited on 24 February 2022. Completion of the last trial participant is expected to take place in early/mid March 2023. Apart from extended participant recruitment, the project is progressing at the time of writing (19 April 2022), according to plan without deviations from current protocol.

Publication and storage of data and biological material.

Blood samples used to measure the serum concentrations are destroyed by the laboratory immediately after the analyses. This applies to all blood samples taken - no biological material is stored or used in a biobank, the blood samples are destroyed immediately after the stated analyzes have been carried out. The Act on the processing of personal data will be complied with. All data will be handled confidentially and published in anonymized form. Raw data and randomization codes will be stored in anonymized form under secure conditions for 15 years after the end of the trial. Study results will be submitted to recognized international journals and both positive and negative results will be published.

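### A post-randomisation switch to galantamine or rivastigmine withdraws the participant, with no later assessment or as-randomised analysis, so the 1-year clinical comparison can be biased

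*Combined protocol and SAP*

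**What the plan says.** The section Withdrawal criteria for all lists, beside the participant's or relative's own wish to leave, "Medical reasons, including if the treatment is changed to an anti-dementia drug for which serum concentrations are not measured in this study"; a bracketed note names galantamine and rivastigmine. Changes between donepezil and memantine do not trigger the clause.

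The list under Inclusion interview/recruitment shows how the tested strategy can lead to such a switch. For intervention participants with early side effects, "The dose is adjusted in relation to the serum concentration, if necessary the dosage and/or drug prescribed is changed". At half a year, "The dosage is adjusted according to the serum concentration, if deemed appropriate an alternative [anti-dementia] drug is prescribed". Side Effects and Adverse Events adds that, in usual care, a drug-related side effect leads to another anti-dementia drug or a lower dose.

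The Recruitment section compares side effects between the groups, "including the proportion of patients who had to change preparations or abandon medical treatment due to side effects". Under Study visits, "If informed consent is obtained, one extra visit to the clinic 1 year after enrollment"; the half-year visit is routine. Adverse events are covered separately: "All adverse events that occur during the study must be monitored and followed until they have either resolved".

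Statistics and power calculation sets 55 per group, 110 in total. It names no analysis population, missing-data method or allowance for withdrawals.

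**The concern.** The reason for the clause is that the new drug is not assayed. That is a reason to stop collecting and analysing serum concentrations. It is not a reason to stop measuring MMSE, ACE, DAD, NPI and CGI.

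The event is not neutral. It happens after randomisation, monitoring may make it more or less frequent, and it is tied to tolerability. The plan itself compares changes of preparation due to side effects between the arms. If switchers drop out of the 1-year scales, the comparison is between groups selected after randomisation.

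The direction is open. If monitoring prevents switches, the intervention arm keeps more poor responders than the control arm, and a benefit is hidden. If monitoring prompts switches, the intervention arm loses poor responders and looks better than it is.

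Side-effect data, the fact of the switch and adverse-event follow-up are still recorded, so no loss is claimed there.

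**Working it through.** **1. Does the text restore switchers to the 1-year comparison?**

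- Study execution and visits calls all participants to the 1-year visit, but does not say whether this includes those withdrawn.
- Ethical considerations has one explicit rule for staying in the protocol. It concerns combination treatment offered after unusual worsening, not these switches.
- Recruitment counts changes of preparation in the side-effect comparison only.
- The 1-year visit goes beyond routine half-year follow-up, so usual care would not supply the missing scores.

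None of these restores the assessment. The flowchart could not be read in the available text.

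**2. The plan's own sample size.** Inputs from Statistics and power calculation: P1 = 0.50, P2 = 0.75, z values 1.96 and 0.84.

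N = (1.96 + 0.84)² × (0.25 + 0.1875) / 0.25² = 54.88, rounded up to 55 per group. This reproduces and is not in dispute. Since 2 × 55 = 110, nothing is added for withdrawals.

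**3. Bias with no true effect.** The documents give no switching rate and no outcome in switchers, so all rates here are assumed. Let sc and si be the control and intervention switching rates, and g the response gap between switchers and others. Assume that those who switch in the lower-rate arm would also switch in the other. Then, for sc ≥ si:

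bias = −(sc − si) × g / (1 − si)

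| Control / intervention | g = 0.20 | g = 0.40 |
|---|---|---|
| 10% / 5% | −0.05 × 0.20 / 0.95 = −1.1 points | −2.1 points |
| 20% / 10% | −0.10 × 0.20 / 0.90 = −2.2 points | −4.4 points |
| 30% / 10% | −0.20 × 0.20 / 0.90 = −4.4 points | −8.9 points |
| 10% / 20% (reversed) | +2.2 points | +4.4 points |
| equal rates, or g = 0 | 0 | 0 |

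Two other models test how far this depends on the form chosen:

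- Equal overall response by arm, with g the gap between switchers and completers within an arm. Bias = (si − sc) × g, which gives −1 to −2, −2 to −4 and −4 to −8 points for the first three rows.
- Switchers g below their arm's average. Bias = g × [si/(1 − si) − sc/(1 − sc)], which gives −1.2 to −2.3, −2.8 to −5.6 and −6.3 to −12.7 points. These are larger because the implied gap between switchers and completers is wider.

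Under this last form, with 50% response in both arms and switchers responding at 20-40%, the observed rate is (0.50 − w × r)/(1 − w), where w is the switching rate and r the switchers' response rate. Switching of 5% control and 15% intervention gives a spurious +1.2 to +3.7 points and a type I error of 5.2-6.6%. Switching of 5% and 25% gives +2.8 to +8.4 points and 5.8-12.7%.

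**4. Power.** Using the plan's formula with n1 control and n2 intervention participants left:

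power = Φ(0.25 / √(0.25/n1 + 0.1875/n2) − 1.96)

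| Loss, control / intervention | n1 / n2 | Power |
|---|---|---|
| none | 55 / 55 | 80% |
| 10% / 10% | 49.5 / 49.5 | 76% |
| 20% / 20% | 44 / 44 | 71% |
| 10% / 5% | 49.5 / 52.25 | 77% |
| 20% / 10% | 44 / 49.5 | 73% |
| 30% / 10% | 38.5 / 49.5 | 69% |

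These figures keep the full 25-point difference. They show lost information only and should not be added to the bias above.

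**5. What could still be recovered.** Recruitment ran from 12 February 2020; "The last participant was recruited on 24 February 2022". That is 743 days. At version 1.9 (19 April 2022), the 1-year visit was still due for those enrolled after 19 April 2021: 311 days, and 311/743 = 42% of the window. This is a share of calendar time and equals a share of participants only if recruitment was even. At the document date, 28 March 2023, all last visits were expected to be complete.

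**The case against.** The strongest reply is that exclusion of switchers is inferred. The text calls all participants at 1 year and tells both groups they will be followed for at least a year. That is fair, and the concern is put no higher than likely. Even so, listing the switch beside a wish to leave the study most naturally means leaving the study, and nothing says otherwise.

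Second, exposure is narrow. Only two drugs trigger the clause, and a change made at the 1-year visit itself costs no outcome data. The Background puts about 80% of treated patients on donepezil or memantine. This is not a switching rate, but it lends no support to 30% of controls leaving both drugs. The 4 to 9 point scenario is an upper illustration.

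Third, the response gap has no source: the text links switching to side effects, not to poor response, and with no gap there is no bias. This stands, as does the point that the figures depend on the model, although the alternatives are of the same order.

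Fourth, the remedy is partly too late, and half-year scale data are not clearly scheduled. The Introduction ties the scales to study visits, and Methods and parameters calls all of them except the CGI routine, so half-year scores are plausible. An early switcher may nevertheless have only baseline data.

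**Conclusion.** The concern holds. A stated rule removes participants for a post-randomisation event that the intervention can influence, and the readable text provides neither outcome follow-up nor an as-randomised analysis for them. The 1-year comparison can therefore be biased in either direction.

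On the nested model the illustrative size is about 1 to 4 points at modest unequal switching and up to 9 points at 30% versus 10%, against a design effect of 25 points. It is zero if switching and switchers' outcomes are equal by arm, or if switchers respond like everyone else. These figures rest on assumed rates and gaps, so confidence is medium. This should be fixed, but on the documents alone it does not invalidate the trial.

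**What to change.** - Reword the withdrawal clause so that a switch to an unmeasured drug ends only the serum-concentration measurements and analyses, not outcome follow-up. Invite switchers, with consent, to any 1-year visit still due for the clinical scales and compliance.
- State that all participants are analysed in the group to which they were randomised.
- Where the 1-year visit was missed, use the data collected (baseline, half-year and any later visit) with multiple imputation. Add a sensitivity analysis that counts switchers as non-responders on the plan's MMSE rule (a decrease of less than 2 points in one year). Fix both before unblinding.
- Report withdrawals by arm and reason.

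The other withdrawal criteria and all treatment decisions stay as they are.

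The cost is one reworded clause and one analysis paragraph; the visit and scales already exist. The rewording helps only visits still due, so at the document date probably only the analysis part remains. The downside is small: some 1-year clinical data would come without a serum value, and imputation would rest on few observed switchers.

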Based on clinical database information, 15-20 newly referred patients eligible for study participation will likely be referred to RVD per month. If it is assumed that approx. half will participate in the project, approx. 100 patients could be included in one year.

If it is assumed that <50% of the participants reach the recommended serum concentration and thus relevant clinical effect on standard dosing (cf. pilot study), and that this can be increased to 75% by dose adjustment after S concentration determination, the following calculation can be performed on the basis of the formula:

$$N > (Z_{2\alpha} + Z_{\beta})^2 \times (P_1(1-P_1) + P_2(1-P_2)) / (P_1 - P_2)^2$$

where N is the number of necessary participants in each group, α is significance level 5%, β is the probability of type 2 error (strength is $1-\beta = 80\%$), P_1 is dose optimization (optimized clinical effect) with regular dosing, P_2 is dose optimization (optimized clinical effect) guided by S-level and possibly side effects.

$$N > (1.96+0.84)^2 \times (0.5 \times 0.5 + 0.75 \times 0.25) / 0.25^2 = 7.84 \times (0.25 + 0.1875) / 0.0625 \sim 55$$

In other words, 110 participants must be included in the project period in order to calculate the clinical utility of serum concentration measurements with the stated assumptions. Realistically this goal for participant recruitment can be reached within a study period of one to two years.

Risk assessment (risks and discomfort)

Blood test

For all participants in the study a single blood sample is collected for genetic analyses. For the intervention group, as stated, a single blood sample is also taken in case of side effects, and after $\frac{1}{2}$ and 1 year. The blood sample is collected in a completely routine manner by a trained professional. The procedure is not associated with any other discomfort or inconvenience, apart from what is known for a routine blood test in a normal clinical context. For the control group, a blood sample is collected at the 1 year follow-up visit, when the CRF is closed for that participant.

MMSE, ACE, GDS, DAD, NPI

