As by custom in ordinary clinical practice [in RVD], all patients and relatives are informed about potential side effects at the start of treatment and dose adjustments. Side effects are routinely reported to the contact nurse by telephone, in practice this happens on the same day or within a few days after side effects occur. In connection with the project, participants in the intervention group will receive the same information about side effects as in routine clinical practice, supplemented by corresponding information about the need to report by telephone to the contact nurse in the event of side effects. Furthermore, all participants are asked about side effects at the ½-year and 1-year follow-up visits. In each individual case, an assessment will be made by one of the clinic's specialists (senior physicians) as to whether side effects should lead to dose reduction or discontinuation. All reported side effects are entered into the participant's CRF. As by clinical routine, all participants and relatives will be encouraged to contact the contact nurse by telephone in case of any suspicion of side effects. If the reported side effects are deemed to be related to the medicine, common practice is to either switch to an alternative anti-dementia drug or reduce the dose. It depends on a medical assessment whether there is a basis for changing the preparation or reducing the dose. In all such cases, in connection with the project, a blood test will be offered to determine the serum concentration. Common side effects (in 1-10% of subjects): Less than 5% of patients who have a blood test will develop a minor hematoma at the insertion site [of the needle]. This side effect is benign and will disappear without any treatment. Slight pain at the injection site itself and subsequent mild soreness may occur. It may occur that participants who are uptitrated in dose on the basis of low serum concentrations will develop side effects. These are mainly mild gastrointestinal side effects, and in rare cases cardiac side effects. Occurrence

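### The side-effects section offers a serum test with no arm or time limit, contradicting the intervention-only rule stated elsewhere; the half-year wording is also ambiguous

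*Combined protocol and SAP*

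**What the plan says.** **The control-arm rule.** The Introduction gives controls ordinary titration and follow-up, with serum determined at 12 months. The Recruitment text gives them one extra sample, at 1 year. Study execution and visits says: "Participants belonging to the control group will not undergo any extra procedures, apart from a single blood test at the end of the project". Risk assessment, Blood test, says: "For the control group, a blood sample is collected at the 1 year follow-up visit".

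**The side-effect test.** Study execution and visits offers it to the intervention group when side effects arise between 2 weeks and 2 months after treatment starts. Risk assessment also lists it for the intervention group. Side Effects and Adverse Events takes a different line. It asks participants and relatives generally to telephone the nurse about any suspected side effect, describes the usual choice between switching drug and lowering the dose, and continues: "In all such cases, in connection with the project, a blood test will be offered to determine the serum concentration". It names no arm and no window.

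**The half-year test.** In Study execution and visits, the bullet that opens with the intervention group goes on to say that at the half-year follow-up "one extra blood test is collected for all participants". The next sentence adjusts dosage to the serum concentration. The Recruitment text has the same structure: it describes the intervention group and then says that *everyone* has an extra test at the half-year and 1-year check-ups.

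**The concern.** A nurse or physician following the side-effects section as written would offer a control participant with a drug-related side effect a serum test that other sections reserve for the intervention arm. One following the half-year sentence literally would test controls at 6 months and adjust their dose on the result.

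Two comparisons are exposed. The first is clinical effect at 1 year, on which the sample size rests. The second is the planned comparison of the occurrence, duration and outcome of side effects, including drug changes and stopping because of them. The unrestricted sentence reaches exactly the control participants who drive that second comparison, at the moment when a switch or reduction is being considered.

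The plan does not say how controls with an early serum result would be listed or described. If the two arms turned out alike, a reader could not tell an ineffective intervention from one that had partly reached the controls.

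**Working it through.** **Setting the sections side by side**

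| Test before 1 year | Given to the intervention group only | Worded without an arm limit |
|---|---|---|
| Side effects | Study execution and visits (2 weeks to 2 months); Risk assessment | Side Effects and Adverse Events (no window either) |
| Half-year | Introduction; Risk assessment | Study execution and visits; Recruitment text (both inside intervention-group descriptions) |

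The first row is a contradiction. The second is an ambiguity. The bullet's opening and the control rule directly after it favour the narrow reading. Against that, the same list uses the expression for both arms when it describes the genetic sample and the 1-year visit, and the half-year visit is routine for everyone, so controls are present when the sentence applies.

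**Reproducing the sample size**

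Inputs from Statistics and power calculation: two-sided 5% (z = 1.96), 80% power (z = 0.84), P1 = 0.50 ("<50% of the participants reach the recommended serum concentration"), P2 = 0.75 ("this can be increased to 75% by dose adjustment after S concentration determination"), and "N is the number of necessary participants in each group".

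N = (1.96 + 0.84)² × (0.50×0.50 + 0.75×0.25) / 0.25² = 7.84 × 0.4375 / 0.0625 = 54.88, so 55 per group and 110 in total. The plan's figure reproduces. It takes controls to receive none of the serum-guided gain.

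**Illustrating dilution**

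Let c be the share of controls exposed early, and assume that each gains the full benefit. Neither c nor the size of the gain in exposed controls is in the documents. Then P1 = 0.50 + 0.25c and, at 55 per arm, power ≈ Φ(d/SE − 1.96), with d = 0.75 − P1 and SE = √{[P1(1−P1) + 0.1875]/55}.

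| c | P1 | d | SE | d/SE | Power |
|---|---|---|---|---|---|
| 0 | 0.500 | 0.250 | 0.0892 | 2.80 | 80.0% |
| 0.10 | 0.525 | 0.225 | 0.0891 | 2.52 | 71.4% |
| 0.20 | 0.550 | 0.200 | 0.0889 | 2.25 | 61.4% |
| 0.30 | 0.575 | 0.175 | 0.0886 | 1.97 | 50.6% |

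Only the product of share and gain matters here. If exposed controls gained half the benefit, 20% exposure would give P1 = 0.50 + 0.25 × 0.20 × 0.5 = 0.525, the 10% row. For a given share, the table therefore shows the loss under full benefit; any smaller gain means a smaller loss.

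**The case against.** **The context can settle the wording.** The half-year sentence sits inside the intervention bullet, just before the control rule. It can mean all intervention participants, as opposed to only those with side effects. In the side-effects section, the project-specific additions are first introduced for the intervention group, and the appeal to participants generally is labelled clinical routine, so an intervention-only reading can be argued there too. Risk assessment states it outright, and the text is a translation. This stands for the half-year sentence, which is why it is called ambiguous and not contradictory. For the side-effect test it makes the intention plausible, but the sentence still carries no arm or time limit and directly follows text about both arms.

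**A test is not the intervention.** The side-effects section leaves the choice between switching and reducing to a medical assessment and does not make the serum value decide. This stands: that sentence would give controls the measurement, which is part of the intervention, but not an explicit serum-guided adjustment.

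**The stronger reading fails.** A reader might infer that controls receive the whole intervention, so that the expected difference is zero and power only 5%. That needs every control to gain the full benefit. The documents do not support it. Explicit serum-guided adjustment for early side effects (Study execution and visits) and the step for unusual worsening (Ethical considerations) are stated for the intervention group only, and nothing shows that a test prompted by side effects yields the 50%-to-75% gain.

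**Some data already exist.** Serum concentration is a listed outcome variable and reported side effects go into the CRF. What is missing is a planned listing by arm and date.

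**Conclusion.** Wrong as written, as an internal contradiction. The side-effect serum test is limited to the intervention group in two sections and unlimited in a third, and the unlimited version also conflicts with the single 1-year serum sample allowed to controls. The half-year wording is ambiguous, with context on the side of the narrow reading.

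The consequence is possible dilution of the contrast, not its removal. The power figures of about 71%, 61% and 51% illustrate that dilution. They rest on assumed exposure shares of 10%, 20% and 30% and on full benefit in exposed controls. The documents do not show that any control was tested early. For the side-effect comparison the plan states no effect size, so no figure can be attached.

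**What to change.** Reconcile the Recruitment text, Study execution and visits, and Side Effects and Adverse Events with the Introduction and Risk assessment, so that each serum test names its arm and its time window. Which clinical rule applies is for the sponsor to state. Recruitment closed on 24 February 2022 and the last participant was expected to finish in March 2023, so the correction may come too late to change conduct; the report should then say which reading was followed.

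In the analysis, keep every participant in the randomised arm. List by arm and date each serum result available before the 12-month visit, and any dose or drug change made after it. Give the share of controls exposed next to the effect estimate and its confidence interval. Do not recompute power at the observed share: that would be post-hoc power, and the interval already conveys the precision achieved.

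The cost is a few wording corrections and one descriptive table. The sample size does not change.
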